8.3 Sample Size

The study sample size is limited to 10 subjects receiving the Basmati Injectrode insert.

9.0 Methods and Procedure

9.1 DATA COLLECTION REQUIREMENTS

Subject data will be collected and documented on case report forms (CRFs). Templates of the CRFs for this study are located in Appendix 17.

9.1.1 Subject Screening Procedure

Subjects will be chosen from healthy volunteer candidates. Potential study participants must pass a thorough general medical exam. Subjects may either be male or female and must meet all the study's eligibility criteria which are typical eligibility criteria for early feasibility studies. They will be required to sign an informed consent form prior to being asked to participate in the study, undergoing any study-related procedures or having any data collection occurring.

Assessments and Data Collection	Screening and Enrollment	Call for patch removal	Injectrode Placement	Follow-up visits	Efficacy and Explant visit	Post study follow-up
Day (relative vs. Placement)	-5 to -4	-2	0	7 ± 2 14 ± 2	28 (-2 to 0)	48 ± 2
● Eligibility confirmation	✓					
● Medical history	✓					
● Physical exam	✓					
● Informed consent	✓					
● Record demographics	✓					
● Verification of absence of allergy to gold & pregnancy test	✓					
● Confirmation of study eligibility	✓					
● Gold skin patch test placement	✓					
● Removal of skin patch		✓				
● Read skin test patch results			✓			
● Basmati placement procedure			✓			
● Ultrasound & Fluoroscopy image capture			✓		✓ (pre & post)	(✓)
● Capture of images of surgical site	✓		✓ (post)	✓ (✓)	✓	✓
● Remove skin suture(s) if placed during surgery						
● Measure impedance needle to needle connection					✓	
● Measure stimulation thresholds					✓	
● Removal procedure					✓	
● Study participant exit						✓

Table 2: Focus on Screening and Enrollment

9.1.2 Informed Consent

Informed consent is defined as legally effective, documented confirmation of a subject's (or their legally authorized representative's or guardian's) voluntary agreement to participate in a particular clinical investigation after information has been given to the subject on all aspects of the clinical investigation relevant to the subject's decision to participate. When a subject signs and dates the informed consent form, he/she is considered a subject enrolled in the study.

Prior to initiation of any study-specific procedures, subjects (or their legally authorized representative or guardian) must sign and date the informed consent form and Health Insurance Portability and Accountability Act (HIPAA) authorization, or equivalent, where required by law and IRB. Documentation that consent was obtained prior to any study-related procedures must be maintained in the subject's case history.

9.1.3 SCREENING and ENROLLMENT VISIT (IN-PERSON, day -5 or day -4)

Once the informed consent has been documented, the study participant's eligibility for study participation is verified at the Enrollment Visit. During this assessment, the study physician will collect and document each potential participant's relevant medical history (including diagnosis), demographics and physical examination results. The visit concludes with the placement of the allergy skin test patch on the arm of the study participant. The gold allergy skin test patch is essentially a small band-aid filled with gold salt. According to the test's instruction for use, the patch must be placed on the skin for two to three days prior to an additional waiting period of two more days before the skin reaction can be interpreted by the physician. Accordingly, the next two visits are scheduled with the study participant as (1) a phone call to remove the skin test while creating a record in the corresponding CRF (see 9.1.4 below) and the (2) actual in-person Insert Placement Visit with a two-day delay following the phone call.

9.1.4 ALLERGY TEST PATCH REMOVAL VISIT (CALL, day -2)

The first follow-up visit is a phone call scheduled for two (three) days after the Enrollment Visit. The study participant is asked to remove the gold allergy skin test patch and a record of the removal is made in the corresponding CRF for that visit. The scheduling of the Insert Placement Visit for two days later is verified with the study participant.

9.1.5

9.1.6 INSERT PLACEMENT VISIT (IN-PERSON, day 0)

The Insert Placement Visit begins with an examination of the study participant's arm to capture and interpret the result of the gold allergy skin test by the physician. Once the absence of a gold allergy is verified, the participant advances to the group of up to 10 participants that will receive the Basmati Injectrode insert.

Appropriately trained field staff will assist as necessary with the Basmati Injectrode insert procedure. The recommended placement location for the device on the left or the right hip region (figure 6) will be determined by the physician and documented on the CRF.

[figure not shown]

Figure 6: Depiction of the surgical location (arrows). Placement of the Basmati Injectrode is the hip region of the study participant at approximately the height of the naval.

Prior to the placement of the insert, the surgical location near the hip, approximately at the height of the naval, is cleaned and sterilized following standard OR procedures (betadine, 70% isopropyl alcohol). Following an injection of subcutaneous lidocaine (1%), a small (~5mm) incision is made using a scalpel followed by blunt dissection of the subcutaneous tissue. Blunt dissection technique is used to create a tunnel of about 3-5 mm diameter, at a depth of approximately 2mm measured from the surface of the skin, and up to 2 cm long (figure 7, A).

[figure not shown]

Figure 7: Approximate dimensions of the tunnel placed at the hip region prior to (A) and following (B) the placement of the Basmati Injectrode insert.

Using the deployment device, the Basmati Injectrode is placed into the distal end of the tunnel, leaving a length of approximately 1 cm of empty tunnel between the Basmati and the skin incision (Figure 7, B). At the clinician's discretion, pressure to the wound channel alone or surgical glue may be used to ensure proper adherence of the tunnel walls to close the length of the tunnel. The skin incision may be

closed with steri-strips, surgical glue or one or more small suture loops as per the physician's discretion.

Pain management will be provided post surgery based on physician discretion.

Information regarding the devices used, location and procedure data will be collected on an Insert placement section of the CRF. With the study participant's and the surgeon's consent, Neuronoff's representative may be present during the insert procedure.

The steps taken during the Injectrode Placement Procedure visit are further outline in the table below:

Assessments and Data Collection	Screening and Enrollment	Call for patch removal	Injectrode Placement	Follow-up visits	Efficacy and Explant visit	Post study follow-up
Day (relative vs. Placement)	-5 to -4	-2	0	7 ± 2 14 ± 2	28 (-2 to 0)	48 ± 2
● Eligibility confirmation	✓					
● Medical history	✓					
● Physical exam	✓					
● Informed consent	✓					
● Record demographics	✓					
● Verification of absence of allergy to gold & pregnancy test	✓					
● Confirmation of study eligibility	✓					
● Gold skin patch test placement	✓					
● Removal of skin patch		✓				
● Read skin test patch results			✓			
● Basmati placement procedure			✓			
● Ultrasound & Fluoroscopy image capture			✓		✓ (pre & post)	(✓)
● Capture of images of surgical site	✓		✓ (post)	✓ (✓)	✓	✓
● Remove skin suture(s) if placed during surgery					✓	(✓)
● Measure impedance needle to needle connection					✓	
● Measure stimulation thresholds					✓	
● Removal procedure					✓	
● Study participant exit						✓

Table 3: Focus on the Injectrode Placement visit

9.1.7 FOLLOW-UP VISITS (IN-PERSON or CALL, day 7 and day 14)

Follow-up visits will occur on day 7 (+/-2) and 14 (+/-2) post-procedure. Data collected at these visits will be recorded on case forms (CRFs) and will include the bolded (grayed) portion:

Assessments and Data Collection	Screening and Enrollment	Call for patch removal	Injectrode Placement	Follow-up visits	Efficacy and Explant visit	Post study follow-up
Day (relative vs. Placement)	-5 to -4	-2	0	7 ± 2 14 ± 2	28 (-2 to 0)	42 ± 2
• Eligibility confirmation	✓					
• Medical history	✓					
• Physical exam	✓					
• Informed consent	✓					
• Record demographics	✓					
• Verification of absence of allergy to gold & pregnancy test	✓					
• Confirmation of study eligibility	✓					
• Gold skin patch test placement						
• Removal of skin patch		✓				
• Read skin test patch results			✓			
• Basmati placement procedure			✓			
• Ultrasound & Fluoroscopy image capture			✓		✓ (pre & post)	(✓)
• Capture of images of surgical site	✓		✓ (post)	✓ (✓)	✓	✓ (✓)
• Remove skin suture(s) if placed during surgery						
• Measure impedance needle to needle connection					✓	
• Measure stimulation thresholds					✓	
• Removal procedure					✓	
• Study participant exit						✓

Table 4: Focus on follow-up visits

9.1.8 EFFICACY & EXPLANT VISIT (IN-PERSON, day 28)

This visit has two parts. The total duration of this visit is expected to be approximately 1 hour.

The first part of the visit is focused on capturing stimulation thresholds of cutaneous afferent nerves to provide information about the Injectrode's capabilities to conduct current at low electrical impedance values. This first part is anticipated to last for approximately 30 minutes and scheduled to occur just before the explant of the Basmati Injectrode insert.

The second part of the visit is the actual explant of the device that will then be sent to histopathology for further processing. This second part is anticipated to last for approximately 30 minutes and will include image capturing for purposes of documentation.

Part I: Impedance and stimulation threshold data acquisition

Materials:

Stimulation will be provided using a DS7A Constant Current Stimulator unit (Digitimer), a device with CE and FDA clearance. Electrical impedance will be measured with a handheld, battery-powered oscilloscope (Fluke ScopeMeter) that is certified and calibrated. Sterile clinical grade standard needles intended for single patient use (30 gauge) will be used to directly interface percutaneously with the Injectrode. Details for this interfacing approach are provided below. A clinical grade, disposable, surface patch electrode will be used as a distal return, referred to as a TENS electrode/patch in this document. The Stimulator, Oscilloscope, Needles and TENS electrodes will be connected together using standard leads (Pamona, Comed).

Methods:

The setup for these stimulation and impedance tests are done under two types of visualization. First, visualization is done via ultrasound according to a Mohs' surgery plan. Second, the setup is visualized with fluoroscopy to ensure that the needles are placed precisely within the subcutaneously implanted Basmati Injectrode.

All equipment will be turned on prior to use, followed by connecting the Stimulator in parallel to the Oscilloscope as shown in Figures 7a through 7e below. Data will be recorded for every measurement. Prior to beginning the measurements, test leads will also be hooked up to the stimulator in parallel. Generally, measurements during this visit will be recorded at a current amplitude ranging between 0.1 and 10 mA and pulse widths ranging from 50 μ sec to 1500 μ sec. Reference impedance values will be recorded at a current amplitude at 1mA and a pulse width of 200 μ sec using a reference resistor of 1 kOhm. The sensory stimulation thresholds ("Measurement 1" through "Measurement 3.3") below will be conducted with a preferred pulse width of 100 μ sec and 200 μ sec, and, if need be, may be measured once more with a different pulse width in the range between 50 μ sec to 1500 μ sec to be able to capture stable measurements.

In order to record sensory afferent nerve responses to electrical stimulation, it is imperative that lidocaine is not injected at the site of the Injectrode for the entity of part 1. Instead, the skin above the

Injectrode is cleaned using 70% Isopropyl alcohol at the site of the Injectrode with a margin of 3cm around the site, identified via palpation of the skin. Two 30 gauge needles are inserted through the cleaned skin into the Injectrode as shown in Figures 8a through 8e. At a location 1-2cm away from the Injectrode, a third 30 gauge needle will be inserted as shown in Figure 8a. Finally, at a location approximately 10 cm away from the Injectrode, a TENS patch electrode will be placed to function as the return electrode for electrical current. Test leads with hooked ends will be attached to the needle shaft extending out of the skin and taped to the skin to keep the leads secure and from pulling on the needles should the study participant or lead move.

Measurement 1: Once the leads are properly attached to the needles and TENS patch, testing may commence. The first measurement will establish the stimulation activation (sensation) threshold of afferent nerves in the skin of the hip region of the study participant in the vicinity of where the Injectrode is present. Needle D and TENS patch C will first be connected to the stimulator (as shown in figure 8a), and step wise increments in stimulus amplitude will be performed until the study participant notes that they can perceive the stimulation (e.g. step size amplitude = 100 μ A, pulse width = 200 μ sec). The study participant will be asked to report when they perceive a paresthesia, essentially a tingling sensation of the skin. The current and pulse width values for the initial report of paresthesia will be recorded and may be verified with a second measurement. The values allowing the study participant to perceive a tingling paresthesia sensation are expected to be an order of magnitude smaller than currents needed to cause the perception of pain. If the study participant reports pain during the stimulation then the clinician will adjust their testing approach accordingly to avoid such participant feedback. Once the stimulation activation threshold is determined, lead D may be unplugged and needle D removed from the skin.

[figure not shown]

Figure 8a: Stimulus activation setup of electrodes for measurement #1.

A series of three stimulation tests will be performed between the Injectrode (A, B) and the TENS patch (C), as shown in Figures 8c, 8d, and 8e. The first stimulation for each measurement will be performed at or below the stimulation threshold established in measurement 1 for the study participant. The study participant will be asked whether they sensed the stimulus, and their answer recorded. If needed, the stimulation current will be increased in increments of 100 μ A of current or 50-100 μ sec of pulse duration until the study participant perceives the stimulus.

In **measurement 2** (Figure 8b), needle A and the TENS surface patch electrode (C) will be hooked up to the stimulator and oscilloscope.

[figure not shown]

Figure 8b: Impedance and Stimulation setup of electrodes for measurement #2.

In **measurement 3** (Figure 8c), needle B and the TENS surface patch electrode (C) will be hooked up to the stimulator and oscilloscope.

[figure not shown]

Figure 8c: Stimulation setup of electrodes for measurement #3.

In **measurement 4** (Figure 8d), needles A and B will be connected together to one output/input, while the TENS surface patch electrode (C) will be hooked up to the other output/input of the stimulator and oscilloscope.

[figure not shown]

Figure 8d: Stimulation setup of electrodes for measurement #4.

Measurement 5: Lastly, needles A and B will be hooked up to the stimulator as shown in Figure 8e. Electrical stimulation at the stimulus activation threshold will be applied. The study participant will be asked if they still perceive the stimulation at threshold. If they do not, another stimulus activation threshold test will be performed (e.g. step size amplitude = 100 μ A, pulse width = 200 μ sec) up to 10 mA of current. After each stimulation, the study participant will be asked if they perceived the stimulation, with perception noted as the stimulus activation threshold of current passing through the injectrode. It is expected that the threshold in Measurement 5 will be at least five times higher than that recorded in Measurement 1, as a result of the conductive injectrode shunting (short-circuiting) current between the two needles, thus making it harder to stimulate nerves near the Injectrode. Recorded data from the oscilloscope will be used to calculate the impedance of the Basmati Injectrode.

[figure not shown]

Figure 8e: Stimulation setup of electrodes for measurement #5.

The resulting table of amplitudes and pulse widths resulting from each measurement will be recorded in the CRF.

This closes part 1 of the efficacy and explant visit. The skin at the location of the Injectrode will now be cleaned once more and prepared for surgical removal of the Basmati Injectrode insert.

Part II: Explant (Device Removal)

Methods:

The explant surgical plan will be verified with images from ultrasound and fluoroscopy taken earlier the same day. The explant is a Mohs style surgery. The injection site is anesthetized via lidocaine (solution 1%), and a sharp cut is made above the Basmati Injectrode. Next, tissue forceps are used to hold onto the device while dissection is performed around the Injectrode in naïve tissue at a target distance of about 0.5 to 1 mm.

Once removed, the explanted Basmati Insert is placed in a glass vial containing Formalin (10% formaldehyde solution), labeled in code with sequential numbers for each study participant in compliance with HIPAA requirements. The subsequent wound is closed, in layers if applicable. The incision is closed with steri-strip, surgical skin glue or sutures as per the surgeon's discretion. The closed wound is then bandaged as per standard protocol.

At no time from explant to histological analysis report generation will Neuronoff, Inc. be in possession of the device, samples, or data. The device will be left in Formalin for 24 hours, at which time the solution will be exchanged for 70% ethanol by the clinical site. The fixed samples will then be shipped to the following location, with email notifications to [name] (CWRU Tissue Resource Core, [contact]) containing the subject "BASMATI Sample Submission" along with shipping tracking information and subject de-identified sample number:

CWRU Tissue Resource Core
Attn: [name]
[name]
[name]
[name]

Histological slides generated by the Tissue Resource Core will then be transferred to an independent third party pathologist ([name], Case Western Reserve University) for analysis and report generation. Once completed, the report and samples will be sent to Neuronoff, Inc. for safekeeping.

Upon completion of the explant, the site once occupied by the Injectrode is again visualized with ultrasound, and then again with fluoroscopy. Both visualizations will be documented.

Summary:

Assessments and Data Collection	Screening and Enrollment	Call for patch removal	Injectrode Placement	Follow-up visits	Efficacy and Explant visit	Post study follow-up
Day (relative vs. Placement)	-5 to -4	-2	0	7 ± 2 14 ± 2	28 (-2 to 0)	42 ± 2
• Eligibility confirmation	✓					
• Medical history	✓					
• Physical exam	✓					
• Informed consent	✓					
• Record demographics	✓					
• Verification of absence of allergy to gold & pregnancy test	✓					
• Confirmation of study eligibility	✓					
• Removal of skin patch		✓				
• Read skin test patch results			✓			
• Basmati placement procedure			✓			
• Ultrasound & Fluoroscopy image capture			✓		✓ (pre & post)	(✓)
• Capture of images of surgical site	✓		✓ (post)	✓ (✓)	✓	✓ (✓)
• Remove skin suture(s) if placed during surgery						
• Measure impedance needle to needle connection					✓	
• Measure stimulation thresholds					✓	
• Removal procedure					✓	
• Study participant exit						✓

Table 5: Focus on Explant visit

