Basic Assessment of Safety and Minimally invasive stimulation via Injectrode (BASMATI)

Title: **BASMATI** - Basic Assessment of Safety and Minimally invasive stimulation via Injectrode.

Protocol number: NCP-01

Device: Neuronoff Basmati Injectrode

Sponsor: **Neuronoff, Inc.**
[name]

Sponsor Contact: [name]
[contact]
[contact]

Investigator: [name]
[name]
[name]
[contact]

Study Sites: The Ohio Pain Clinic
[name]
[name]
[contact]

Medical Monitor: Kettering Health Network
Kettering Innovation Center
[name], PHD
[contact]

Revision	Revision Date	Sections Revised	Description	Person Issuing Change	DCO#
A	20201012	All	Initial Release	[name]	0041

Confidentiality Statement

This document contains confidential information that is the property of Neuronoff, Inc. and is subject to all of the restrictions on use and disclosure contained in the study contract to which this is appended. Do not copy, disclose, circulate or use for benefit for any third party without written authorization from Neuronoff, Inc.

Protocol Synopsis

Sponsor	Neuronoff, Inc.
Contact Information	[name]
Title of Trial	BASMATI - B asic A sessment of S afety and M inimally i nv A sive s Timulation via I njectrode.
Objective	The objectives of this non-significant risk (NSR) study are to evaluate the safety of the short term placement of the Basmati Injectrode for up to 28 days and the efficacy of conducting electrical current to stimulate subcutaneous nerves on the explant date just prior to explant.
Clinical Hypothesis	The 28 day temporary placement of a Basmati Injectrode does not result in unexpected levels of inflammation or encapsulation.
Investigational Device	A proprietary bio-electronic medical device (Neuronoff Basmati Injectrode Insert) which is capable of transmitting small electrical currents to stimulate sensory nerves.
Study Device description	The Basmati Injectrode is a gold wire coil formed into the shape of a grain of rice of 10mm length by 4mm width by 2 mm height. This gold material is of 99.99% purity and used in predicate medical devices as lead or electrode material in neuromodulation applications.
Comparative Data	Histopathological report describing findings in rodents with sub-chronic and chronic placement of the Injectrode (REC-020).

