1.5 Comparison to earlier studies

The Basmati Injectrode will be placed subcutaneously in up to 10 healthy volunteers for a duration of up to 28 days. On the last day of the study, the Basmati Injectrode will be explanted with a margin of approximately 1mm of healthy tissue utilizing a Mohs surgical approach, ensuring maximal study participant safety while enabling the collection of histological samples for chronic human biocompatibility data. Just prior to explanting the device, two very small 30 gauge needles (similar to electro-acupuncture needles) will be placed approximately 5mm into the skin at the location of the subcutaneously placed Basmati, thereby forming an electrical interface with the Basmati. Electrical impedance and stimulation thresholds for subcutaneous afferences (sensory nerves) will be recorded with the two needles and a TENS electrode patch placed extracorporeally at a distance of approximately 10 cm from the Basmati location.

This approach is similar to that utilized with the StimRouter Neuromodulation System, which also consists of an implanted lead with external stimulation equipment to activate the lead transcutaneously^{3 4 5}. Both systems utilize minimally invasive implantation techniques, with the probe injected via hollow stainless steel tubes^{6 7}. However, the Injectrode is different in that it is presented as a gold mesh as opposed to a fixed metal coil, which allows for improved in-body conforming and thus better reach of potentially hard-to-access anatomic targets. Also, in the least invasive use case, the Injectrode can be stimulated via an external TENS unit without requiring an implanted stimulation cable. Thus, the Injectrode offers improved placement potential and functionality with similar or lesser invasiveness than available technologies.

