2.2 Secondary Outcome Measures: Interfacing Efficacy

Secondary measures focus on device effectiveness. These will include impedance and stimulation threshold measurements for subcutaneous afferent nervous tissue.

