3.0 DEVICE

3.1 Neuronoff Basmati Injectrode insert

This Clinical Non-Significant Risk (NSR) Study will focus on the placement, interfacing with and histopathological assessment of the Basmati Injectrode.

The Basmati Injectrode insert (figure 3) is a mesh formed from gold wire of 99.99% purity, a widely used material in medical devices, offering excellent biocompatibility combined with chemical, mechanical and electrical longevity when implanted into the human body^{8 9 10 11}. The conductive mesh is fabricated from wire with a nominal diameter of 25 microns and at a size of 4 mm width by 10 mm length at about 1.75 mm thickness. This size is similar to a cooked grain of basmati rice.

[figure not shown]

Figure 3: Basmati Injectrode insert is about the size of a grain of rice.

⁸ Geddes, L.A., Roeder, R. Criteria for the Selection of Materials for Implanted Electrodes. *Annals of Biomedical Engineering* **31**, 879–890 (2003). <https://doi.org/10.1114/1.1581292>

⁹ Hielm-Bjorkman A, Raekallio M, Kuusela E, Saarto E, Markkola A, Tulamo RM. Double-blind evaluation of implants of gold wire at acupuncture points in the dog as a treatment for osteoarthritis induced by hip dysplasia. *Vet Rec.* 2001;149(15):452-456.

<https://doi.org/10.1136/vr.149.15.452>

¹⁰ Product: Soft Tissue Marker, Composed of 99.95% Gold
https://www.accessdata.fda.gov/cdrh_docs/pdf3/k031206.pdf
https://www.accessdata.fda.gov/cdrh_docs/pdf9/K091645.pdf

¹¹ Product: Gold Eyelid Weight Implants, Composed of 99.99% Gold
https://www.accessdata.fda.gov/cdrh_docs/pdf/K971242.pdf
https://www.accessdata.fda.gov/cdrh_docs/pdf15/K150986.pdf

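### Sensation in Measurements 2-4 cannot be clearly attributed to the Injectrode: needle insulation is not stated, and the needle-only comparator (needle D) has no stated depth

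*Protocol*

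**What the plan says.** Section 2.2 defines the secondary outcome as "impedance and stimulation threshold measurements for subcutaneous afferent nervous tissue", and section 5.0 places those nerves around the insert. The opening of section 9.1.8, however, describes Part I as capturing thresholds of cutaneous afferents, as information on how well the device conducts.

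The needles are described in 9.1.8 as "Sterile clinical grade standard needles intended for single patient use (30 gauge". The electrical connection is on the shaft: "Test leads with hooked ends will be attached to the needle shaft extending out of the skin". Nothing in the text mentions insulation, a coating or an exposed-tip length. Lidocaine is deliberately withheld during Part I.

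The dimensions are spread over four places:
- Section 1.5: the needles "will be placed approximately 5mm into the skin at the location of the subcutaneously placed Basmati".
- Section 9.1.6: the operator will "create a tunnel of about 3-5 mm diameter", "at a depth of approximately 2mm measured from the surface of the skin".
- Synopsis: the device is "10mm length by 4mm width by 2 mm height".
- Section 3.1: it is "4 mm width by 10 mm length at about 1.75 mm thickness".

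Five measurements follow in 9.1.8. Measurement 1 uses needle D, also 30 gauge, 1-2 cm from the device, against a surface patch. Its depth is not given. Measurements 2, 3 and 4 use needle A, needle B, and A and B joined, each against the same patch, starting at or below the Measurement 1 threshold. Measurement 5 passes current between A and B and is expected to need at least five times the Measurement 1 threshold. No expected result or reading rule is given for Measurements 2-4.

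**The concern.** A conducting shaft has to cross skin before it reaches the device. In Measurements 2-4 the participant reports only whether the stimulus is felt, and that report does not separate current leaving the shaft in the skin from current leaving the device surface. Yet 9.1.8 describes these tests as stimulation between the Injectrode and the patch, and section 2.2 presents the thresholds as those of subcutaneous afferents.

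The readings are taken once, just before explant, in at most 10 people, and section 1.4 says they are meant to support a follow-up study. If the comparator is not matched and the attribution is not limited beforehand, this cannot be repaired later.

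**Working it through.** The protocol gives no figure for exposed shaft, so there is none to reproduce. The check has four steps.

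**1. Share of inserted length outside the device.** Inputs: insertion 5 mm (1.5), top of device at 2 mm (9.1.6), height 2 mm (Synopsis) or 1.75 mm (3.1). For a perpendicular needle crossing the full height, outside share = (insertion - height) / insertion.
- Height 2 mm: (5 - 2)/5 = 60%, made up of 2 mm above the device and 1 mm below it.
- Height 1.75 mm: (5 - 1.75)/5 = 65%.

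**2. How far this moves.** Every dimension is approximate.

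| Variation (height 2 mm unless stated) | Outside share |
|---|---|
| Tip stops at lower face (4 mm inserted) | 2/4 = 50% |
| Tip stops mid-device (3 mm inserted) | 2/3 = 67% |
| 60° or 45° insertion, 5 mm | 54% or 57% |
| 30° insertion, 5 mm | 80% |
| Device on edge (4 mm vertical), top at 2 mm | 2/5 = 40% |
| Device top at 3.5 mm | 3.5/5 = 70% |

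About 60% is a fair central value, within roughly 40-80%. At the extreme, if the tunnel roof is at 2 mm and the device lies on the floor of a 5 mm tunnel, it spans 5-7 mm and a 5 mm needle only touches its top. That conflicts with the imaging-guided placement in 9.1.8, so I give it no weight beyond showing that 1.5 and 9.1.6 do not fit together under every reading.

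**3. Share of current.** Needle radius is an assumption (0.125-0.16 mm), because only the gauge is given.
- Exposed shaft area for 3 mm: 2π × 0.125 × 3 = 2.4 mm² to 2π × 0.16 × 3 = 3.0 mm² per needle.
- Device envelope: 2 × (10×4 + 10×2 + 4×2) = 136 mm². At 1.75 mm height it is 2 × (40 + 17.5 + 7) = 129 mm².

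A boundary-element calculation treated needle and device as one conductor at a single potential, in uniform tissue under an insulating skin surface. It gave a ratio r of mean current density on the shaft to that on the device of 1.07-1.22. Share of current by the shaft = r × shaft area / (r × shaft area + device area).

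| Case | Calculation | Share |
|---|---|---|
| One needle, radius 0.125 mm | 1.20×2.36 / (1.20×2.36 + 136) | 2.0% |
| One needle, radius 0.16 mm | 1.07×3.02 / (1.07×3.02 + 136) | 2.3% |
| One needle, radius 0.155 mm, device 1.75 mm | 1.21×3.17 / (1.21×3.17 + 129) | 2.9% |
| A and B joined, radius 0.125 mm | 1.22×4.71 / (1.22×4.71 + 136) | 4.1% |
| A and B joined, radius 0.16 mm | 1.09×6.03 / (1.09×6.03 + 136) | 4.6% |

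This gives about 2-3% in Measurements 2 and 3 and 4-5% in Measurement 4.

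**4. What a threshold would mean.** Assume needle D is also 5 mm deep and the set current is I. Mean density on D at radius 0.125 mm is I/(2π × 0.125 × 5) = 0.255 I per mm². On shaft A it is 0.020 I/2.36 = 0.0085 I, about 30 times lower. At radius 0.155 mm with the 1.75 mm device it is 0.205 I against 0.029 I/3.17 = 0.0091 I, about 22 times lower. So:
- With good contact, a threshold near Measurement 1 is hard to explain by leakage from the shaft.
- With poor contact, A or B behaves much like D, and a threshold near Measurement 1 would be expected.
- With good contact and a raised threshold, shaft and device carry similar density, so the reading does not show where the sensation arose.

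**The case against.** The strongest reply is that length is the wrong quantity. A reader might infer from the 60% that most of the current bypasses the device. The documents do not support that: the device's surface is so much larger that, with good contact in uniform tissue, nearly all the current leaves through it. This stands. It depends on the idealisation, though. Section 1.7 reports fibrous capsules in the animals, and the documents give no resistance for a capsule or for the needle-device contact. Either could raise the shaft's share.

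A reader might also infer that a Measurement 2-4 threshold close to Measurement 1 would be counted as a success, or that the secondary objective cannot be answered at all. Neither follows. The protocol has no success rule for Measurements 2-4; it records amplitude, pulse width and the participant's answer. Impedance is part of the outcome, Measurement 5 tests conduction through its shunting effect, Measurement 1 is a needle-only reading nearby, and fluoroscopy checks that the needles are in the device. These address much of the objective. They do not show where a sensation arose, and Measurement 1 is weakened as a comparator by its different site and needle D's unstated depth.

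Two further replies have some force. Section 9.1.8 itself names cutaneous afferents as the readout, so skin sensation is not purely a contaminant there; but that disagrees with 2.2 and 5.0 rather than settling the matter. And bare shafts are inferred from silence: Figures 8a-8e are not available here and may specify the needles. Finally, 2 mm against about 1.75 mm is compatible with rounding and is not an error in itself.

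**Conclusion.** The point holds in a limited form. As the text stands, perceived sensation in Measurements 2-4 cannot be clearly attributed to subcutaneous nerves recruited from the Injectrode surface. About 60% of the inserted length (roughly 40-80%) lies outside the device. The corresponding share of current is only about 2-5% under uniform tissue, good contact and the assumed needle radius, and it is unknown otherwise. The conclusion rests on the shafts being uninsulated, which the text suggests but does not state. It touches one part of a secondary outcome in an unpowered pilot; conduction through the device can still be judged from impedance and Measurement 5. It is a cheap improvement that changes what the trial may conclude, not a flaw that invalidates the visit.

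**What to change.** In section 9.1.8:
- State whether the needle shafts are insulated. Use the same needle type for A, B and D, with D inserted to the same recorded depth as A and B, so that Measurement 1 is a matched needle-only comparator for Measurements 2-5. The factor of five expected in Measurement 5 depends on it too.
- Record needle depth from the ultrasound and fluoroscopy already planned.
- Report Measurements 2-4 as needle-plus-Injectrode thresholds, read within subject against Measurement 1 and beside the A-B impedance as a contact check. Do not attribute them to the Injectrode or to subcutaneous afferents alone.
- Reconcile the cutaneous readout in 9.1.8 with the subcutaneous one in 2.2 and 5.0, and the insertion depth in 1.5 with the placement depth in 9.1.6.

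Partly insulated needles are an option, not a requirement. They may need a different lead connection, and insulating D would change Measurement 1's stated purpose as a skin threshold. Otherwise the cost is a few sentences, one more recorded value per needle, and a slightly weaker claim for one part of the secondary outcome.
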